Healthy subjects will be consented and screened for eligibility. Then, participants will perform a logical memory test, immediate recall test, and 25 minute recall. Participants will also perform a verbal fluency test. KVLT-R and BVMT-R and Rey Complex Figure test (RCFT).

Visit 2

Healthy subjects will perform the 1 week retrieval for the logical memory task, be given instructions for the scan test, and undergo the first set of MRI and fMRI scans.

Visit 3

Healthy subjects will complete the second set of MRI and fMRI scans.

Visit 4

Subjects will perform a memory recall task from the fMRI scan on visit 3 and a story segmentation task based on the fMRI scan on visit 2..

Data Analysis and Data Monitoring

Analysis Plan:

Primary: Between treatment differences in PSYRATS Delusions Subscale

Mean effects in week 12. The mean effect of DCS + CBT compared to Placebo + CBT on delusions will be tested using a linear mixed model repeated measures (MMRM) analysis of modified PSYRATS with fixed terms for study visit, DCS/Placebo treatment group and visit by treatment interaction. The model will include random subject effects. Baseline PSYRATS will be included in the model together with a baseline by treatment interaction term. The MMRM will assume a means model, an unstructured covariance matrix and parameter estimation will be based on restricted maximum likelihood. Because of the potential for failure of model convergence due to the requirement of a large number of interaction terms, only a few other covariates will be considered. These may include baseline SANS total score and demographic variables including age and gender, which may be predictive of outcome. To test treatment difference in change from baseline in PSYRATS, we will use a-pairwise contrast on the terms for DCS treatment by visit interaction. To examine differential treatment effects at each CBT week if there is significant interaction, we will perform tests of simple main effects. A significantly larger 12-week decline in mean PSYRATS total score for subjects receiving DSC supports the

Study #:S12-02991

effectiveness of DCS. The probability of a type one error, the size of the test, will be controlled at 0.05, and all tests will be two-tailed. Overall alpha will be maintained at 0.05 for analyses of primary parameters. No adjustments will be made for multiplicity among secondary parameters analyzed. *Missing data*: The analysis will utilize the intention-to-treat principle. All randomized subjects, both completers and non-completers, will be included in the analysis without imputation. Estimates will be unbiased if follow-up data that are missing are "missing at random" conditional on the observed data and model assumptions.

Secondary: Characterizing onset and duration of effectiveness of DCS

a and b. Testing equality of the distributions of onset and duration. Onset is defined as the first week at which the criterion for response is met that lasts at least to the final week of the treatment period. Kaplan-Meier estimates of the survival distributions of time to onset of response will be obtained and the survival distributions will be compared using the log-rank test. The survival distribution, $H(t)$, is the probability that onset will occur after time t . Duration is defined as the number of weeks from onset to offset. Offset for a responder is the first week at which the criterion for response is no longer met. The treatment specific survival distributions of duration will similarly be compared using the log-rank test. The null hypothesis for the second primary outcome measure is that there is no difference between the two treatment groups in the proportion of subjects who are responders (defined as a 20% or greater reduction in PSYRATS Delusions Subscale total score) beginning in week two to the end of the treatment phase. The statistical analysis will be based on a repeated measures logistic regression model. The independent terms in the model will include the same variables and covariates used in the MMRM analysis. By the definition of responder, there cannot be any missing data.

c. Characterizing the population of responders. An alternative approach to characterizing onset when there is a substantial fraction of the population who will never respond is to use a "cure model" (48, 49). The approach was recommended by consensus, in a specially organized conference to develop an approach to measuring onset in GAD (49). The recommended model assumes that $H(t) = (1-p) + pS(t)$ where $H(t)$ is the survival distribution for the full population, $S(t)$ is the conditional survival probability of onset, given that onset will occur and p is the probability that onset will occur e.g., that the subject is a responder. In the parametric approach, the probability of response, p , will be modeled with a logistic and $S(t)$ will be modeled with a Weibull. The equality of the values of p for placebo and DSC will be compared using a likelihood ratio test. There are many tests of equal conditional survival distribution summarized in Laska (49). In the statistical models for p and for $S(t)$, baseline variables can be included as covariates. Those that are statistically significant and that have high influence will be used to identify the population of patients most likely to be responders in subsequent trials. Nonparametric estimates of the probability of response at the end of the treatment period and of the conditional survival distribution of onset for those achieving onset can also be obtained to confirm the results of the parametric model. The Laska-Meisner test will be used to test equal probability of achieving onset (50). (Remove the current 50 and change reference 51 to 50)

Tertiary: Identify mediators of delusional response to DCS

a. Memory Consolidation Hypothesis. The primary MMRM model described above will be used to test the predictive value of 7-day delayed thematic recall on the Logical Memory Test after the first dose of DCS. The baseline covariates in MMRM analysis of modified PSYRATS, will be augmented by the recall value. If statistically significant, a test of the hypothesis that the coefficient of the recall term in the model is not zero will demonstrate the predictive value of the measure. The magnitude of the coefficient is a measure of the degree to which the variable effects the PSYRATS score at week 12. The data for this analysis is restricted to those subjects randomized to DCS.

b. Cognitive Flexibility Hypothesis. Just as for the memory consolidation hypothesis, the primary MMRM model described above will be used to test the predictive value of change in the number of alternative beliefs generated during the first and second administrations of the Alternative Beliefs Exercise in the DCS group on the week 12 PSYRATS score. The baseline covariates in MMRM analysis of modified PSYRATS, will be augmented by the change score.

c. Synergy Hypothesis. The primary MMRM model described above will be used to test whether

Study #:S12-02991

positive outcomes on both the 7-day delayed thematic recall measure and the change in the number of alternative beliefs measure produces better outcomes on the week 12 PSYRATS score than would be expected by additivity. The analysis will also investigate whether outcomes needs to be positive in both variables for the DCS treatment to be effective. In this analysis, the model will contain both covariates and an interaction term. If the interaction term is statistically significant, the sign of the estimated coefficient will indicate synergy/antagonism and the magnitude of the coefficient together with the magnitude of the coefficients of the recall and change measure quantifies the joint effect on the PSYRATS week 12 score.

Data Storage and Confidentiality:

Data Management and Quality Assurance: The Principal Investigator has extensive experience in conducting clinical research studies. Based upon this experience, a comprehensive data management methodology combined with strong planning, control, coordination and quality assurance functions will be implemented. The primary objectives of the data management methodology are to insure the completeness, accuracy and overall integrity of the study data.

Easy to complete case report forms (CRFs) will be developed to standardized data collection across all subjects. Most CRFs will be forms used in previous studies that have a track record of successful data collection. The database will be maintained by the project coordinator, [name] and will be stored in her and the research assistant's office. To protect confidentiality, all information will be identified by code only. DNA samples will be encoded with a numeric study ID and the name of the patient will then be stored in a password protected database that only the research staff will have access to. DNA samples will be stored indefinitely at the NYU CORE lab. Subjects have the option during consent to allow DNA samples to be stored and used for future research related to schizophrenia. Genetic tests will not be shared with the participants or their clinicians, nor will the results be placed in the patient's medical records. Additionally, results from the study will not be released to participants. Data that are identifiable (consent forms, laboratory results, study roster and key) will be stored separately in a locked drawer in these offices. All databases will be password-protected. Coded information will be entered and stored in two secure, password-protected, databases. Subject name or any other personally identifying information will not be stored in either of the databases. Although subject date of birth will be entered into our database for administrative purposes, this information will not be viewable and will not be shared with anyone.

Once data collection has started, staff will review all data, with a special focus on the primary outcome measures and safety data. Missing fields and forms are reviewed to ensure that research staff are collecting data as instructed by the protocol, and entering data into the study database within the recommended time frame. All data are reviewed for accuracy, completeness and logical consistency. Inconsistencies are documented as data management queries. Trends in the queries are monitored and intervention strategies generated to resolve any data issue. Final data clean up will be completed shortly after the last subject visit and the study database will be locked and provided to the study statistician for analyses.

Study recruitment, enrollment, and retention will be monitored to insure that recruitment goals are attained. Study screening information is reviewed by comparing the characteristics of subjects enrolled versus screened out, assisting with potential strategies to improve study enrollment. The ratio of screened to randomized subjects is also reviewed to reflect the effort required to successfully enroll subjects in the study. Research study visit attendance will also be monitored on an ongoing basis.

Estimation of statistical power: We will enroll up to 100 subjects until 60 are evaluable, defined as completing the week 3 clinical assessment which is the first clinical assessment following study drug administration. Subjects will be randomly assigned to DCS or Placebo in a 1:1 ratio. This sample size provides greater than 85% power to detect an effect size of 0.8 in the two-group mean comparisons of 12-week PSYRATS Delusions Subscale total score, which we consider to be clinically-significant. We found an effect size of 0.8 for the difference between treatment groups in our two-session pilot trial and expect a substantially larger effect with 10 DCS-facilitated CBT sessions in this trial. Further, the sample size provides greater than 95%

Study #:S12-02991

power to detect a difference in the response rate of DCS vs placebo assuming the response rate for placebo is 10% and the response rate for DCS is 50%.

Risk/Benefit Assessment

Potential Risks: Loss of confidentiality regarding psychiatric or medical information is a possible risk for which precautions will be taken. Phlebotomy may cause soreness, bruising, bleeding and rarely, infection. A single dose of D-cycloserine 50 mg combined with CBT was well-tolerated in one cross-over study of 20 subjects exposed to drug and weekly dosing of D-cycloserine; 50 mg was well-tolerated in two studies of schizophrenia patients (n=38 subjects exposed to DCS) and in eight studies of anxiety disorder patients. However, it is possible that D-cycloserine could worsen symptoms of schizophrenia. At high doses (500-1,000 mg/d) used for the treatment of tuberculosis, D-cycloserine has been associated with confusion, lethargy, and seizures. High dose, long-term daily administration of D-cycloserine has also been associated with B12 and/or folate deficiency anemia (macrocytic anemia). It is also possible, although unlikely, that CBT will cause anxiety or agitation, insofar as it will entail participants examining their delusional beliefs.

Protection against Risks: All patients are carefully screened to avoid enrollment of anyone for whom study procedures or study drug would be potentially harmful, including subjects with unstable medical or psychiatric illness, recent substance abuse, anemia or insufficient renal function. Subjects will be evaluated by a physician during screening and after the last dose of D-Cycloserine. A complete blood count (CBC) will additionally be performed at screening and after the last dose of D-Cycloserine. If the hemoglobin drops below 13.5 mg/100 ml for male or 12 mg/100 ml for female subjects with a mean corpuscular volume (MCV) greater than 100 (macrocytic anemia consistent with B 12 or folate deficiency), the anemia will be evaluated and treated as clinically indicated. The Side Effect Checklist for assessment of drug side effects will be administered at every visit and neurological side effect scales will be completed monthly. All information will be identified by code only. Data that are identifiable (consent forms, laboratory results, study roster and key) will be stored separately. All databases will be password-protected. Study drug will be suspended if significant clinical worsening is detected by formal assessment or clinical observation. The CBT protocol will be designed to avoid the triggering of excessive anxiety or stress. In addition, a DSMB will review the protocol prior to initiation and will monitor safety during the trial.

Justification of Potential Risks: The risks associated with this trial are minimal and the potential scientific and clinical benefits are considerable. Appropriate safeguards will be in place to ensure that the risk does not outweigh the scientific benefit.

Potential Benefits to the Subjects: All subjects will receive a comprehensive psychiatric and medical evaluation and optimal clinical treatment as part of the NYU/Bellevue Outpatient Psychiatry Department. They will also receive a CBT intervention which is not routinely available. Subjects will be closely monitored for safety. It is possible that subjects randomized to d-cycloserine may benefit with an improved clinical course, although this potential benefit has not been established by prior research.

Subject Identification, Recruitment, and Consent/Accent

Method of Subject Identification and Recruitment: The research team's psychiatrists and psychologist are credentialed treating clinicians at the Bellevue Hospital outpatient clinic where these patients will be referred for or are currently receiving standard psychiatric care, and are part of the treating team for clinical care purposes. In order to further insure protection of privacy for this patient population, patients will not be contacted by any member of the research team unless they have agreed to hear about the research process beforehand from the initial treating clinician. Clinicians in the Outpatient Psychiatry Clinic, Inpatient Psychiatry Units and the Comprehensive Psychiatry Emergency Program at Bellevue Hospital will be provided with flyers

as well as a document listing the inclusion/exclusion criteria in order to facilitate recruitment. This will allow the initial treating clinicians to help identify potential subjects as well as provide interested individuals with basic study-related information. Potential subjects identified by the initial treating clinicians will be asked whether they would like to speak to a researcher. If the patient agrees, the initial treating clinician will then contact the study psychologist and they will determine whether the study clinician (psychologist or psychiatrist) will go and meet with the patient at that time or whether they will meet with the patient during the next scheduled clinic appointment. During this meeting, the study will be explained to the potential participant and in the event that the individual is interested in participating, s/he will then be given the consent form to read and review. In addition to the study consent form, participants will be given a second consent form asking them to participate in providing anonymous quotes to be used in the research group's website for advertisement purposes. All recruitment and screening will be conducted only during the face to face consenting process.

Process of Consent: Patients who are interested in participating in the study will meet with a doctoral level member of the study staff who will review the consent form and assess the patient's capacity for participation in research in accordance with our standardized research procedures. After signing consent, participants will be assessed for eligibility. Subjects will be remunerated for each study visit in amounts commensurate with the time commitment. Reimbursement will also be provided for participant travel expenses to and from the study site.

Subject Capacity and Subject/Representative Comprehension: Subjects capacity for participation in research will be reviewed by a doctoral level member of the study staff during the consenting process as well as by a psychiatrist on staff. The clinician obtaining the informed consent will take steps to ensure that the participant is capable of consenting and participating in the study. The clinician will ensure that the individual understands the content and procedures of the study, their rights as a participant, and their right to discontinue participation at any time. Individuals who are not able to demonstrate this level of comprehension will be excluded from participation. In addition, the potential subject must also achieve a perfect score on a ten-item true/false quiz that asks questions about the study procedure and potential risks. After the consent form has been signed, the subject will be provided with a letter detailing study-related information and contact information for key study staff.

Debriefing Procedures: The only information withheld from subjects is whether the type of medication they are on is active drug or placebo. Subjects will understand that they are blinded.

Consent Forms: Consent forms will be stored in a personal file with the patients initials. This file will be separate from any of the subject's study data in order to separate their data from any identifying information.

Costs to the Subject: There are no costs to the subject associated with the study. Transportation will be reimbursed. Study procedures are paid for via an NIMH grant.

Payment for Participation: Total compensation for the study will be \$400.00. Compensation breakdown is as follows:

▪ \$10 for visits 2, 4, 8, 9, 10, 12, 13, and 14	\$80
▪ \$30 for the screening visit, visits 3, 7, 11, 15, 16, and 17	\$210
▪ \$50 for the first MRI	\$50
▪ \$60 for visit 6	\$60

TOTAL: \$400.00

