 - b. Persistence Hypothesis: DCS improvement of delusions compared to placebo will persist at 3 and 6 month follow-up as defined as maintenance of a 20% or greater reduction in the PSYRATS Delusions Subscale total score from baseline.

Tertiary

3. Identify mediators of delusional response to DCS.
 - a. Memory Consolidation Hypothesis: Change in 7-day thematic recall on the Logical Memory Test after the first dose of DCS will predict improvement on the PSYRATS Delusions Subscale total score at 12 weeks.
 - b. Cognitive Flexibility Hypothesis: Change in the number of alternative beliefs generated during the first compared to the second administration of the Alternative Beliefs exercise in the DCS group will predict improvement of the PSYRATS Delusions Subscale total score at 12 weeks.
4. Identify neural differences in patients compared to age-matched healthy control population.
 - a. Network connectivity hypothesis: Decreased connectivity between the hippocampus and prefrontal cortex in patients at rest and during encoding of stories

Study #:S12-02991

and images, DCS enhancement of connectivity.

b. Memory Hypothesis: Patient impairment of network connectivity will predict performance on immediate and 1-week delay memory relative to healthy controls

Background Significance:

Public Health Significance: Delusions remain a serious public health problem, with persistent antipsychotic-resistant delusions present in approximately 30% of schizophrenia patients. In addition, most patients experience intermittent psychotic relapse associated with major disruptions in rehabilitation and recovery. Persecutory delusions are associated with great psychological distress to patients and family members, whereas other forms of delusions commonly result in social and vocational disability, incarceration, and can result in harm to self or others.

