CBT/DCS Protocol: Individual manualized CBT sessions will last 50 minutes and will be offered weekly for 12 weeks. The first two sessions will focus on engagement, characterization of delusions, and formulation of a treatment plan. Sessions 3 & 4 will consist of an alternative beliefs exercise as employed in our pilot trial in which subjects are trained to produce as many explanations as possible for a series of benign social vignettes (e.g., a taxi driver is staring at you), culminating with their own delusional belief (32). The exercise is structured with a fixed set of vignettes which allows us to record the number of alternative explanations generated by the subject during the exercise as a measure of cognitive flexibility. The remaining 8 sessions will include exploration of antecedents of delusional beliefs, development of a normalizing rationale, cognitive restructuring, testing of explanatory models, and review and consolidation. Study drug (DCS 50 mg or matching placebo) will be administered orally, 1 hour prior to sessions 3-12. Placebo will be administered prior to sessions 1 & 2. DCS and matching placebo capsules will be formulated by the NYUMC research pharmacy.

If a subject misses three consecutive study visits and corresponding CBT sessions, he/she will be withdrawn from the study. These missed visits and sessions may compromise the integrity of the study data and adversely affect the therapeutic alliance which is important in the CBT treatment.

CBT will be provided by [name], a PhD psychologist who trained under [name] at MGH using manualized CBT protocols. A second PhD level therapist may be added and will have at least one year of intensive CBT training and experience working with psychosis. To ensure that there will be no effect due to CBT therapist, balance will be maintained such that each therapist will be assigned to the same number of subjects assigned to DCS as to placebo. This will be accomplished by a statistician independent of the study. Before initiation of the study, training will be provided by [name] who will also provide weekly supervision by video-

Study #:S12-02991

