conference and will monitor treatment fidelity by evaluating audiotapes from 20% of sessions using the Cognitive Therapy for Psychosis Adherence Scale (CTPAS) (34). [name] recently participated in the development of the CBT protocol and conducted trainings for the NIMH-funded RAISE Study. Competency will be defined as a score of at least 10 on the CTPAS. Competency must be achieved by each study therapist with a pilot case prior to participation in the study and must be maintained throughout the study. Additional training will be provided if CTPAS scores drop below 10.

Rationale for DCS/CBT protocol design: The design of our protocol for combining DCS with CBT follows from several findings: 1.) DCS effects may decrease over time with repeated dosing (21) although we believe that once-weekly dosing reduces the risk of tachyphylaxis, 2.) DCS is effective for novel learning only (22) and 3.) we previously found large effects when DCS was combined with the first of two sessions of an alternative beliefs exercise which was designed to exploit DCS effects on memory consolidation and cognitive flexibility (32). Therefore, we will begin with two introductory sessions unaccompanied by study drug; study drug will first be administered with an alternative beliefs exercise at session #3. We will then continue weekly study drug administration one hour prior to CBT sessions and will follow session #3 with a second session of the alternative beliefs exercise in order to replicate the intervention provided in our pilot trial (two consecutive sessions of an alternative beliefs exercise) since delusions continued to improve following the second exposure to the exercise. The remaining 8 sessions will consist of standard CBT approaches to delusions to consolidate therapeutic effects.

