The SAPS will be performed at screening and four weeks later at baseline to identify subjects with persistence of sufficient delusional severity to enter the study. The clinical assessment battery will be comprised of the Psychotic Symptom Rating Scale (PSYRATS), Brief Psychiatric Rating Scale (BPRS), Scale for Assessment of Negative Symptoms (SANS), Calgary Depression Scale for Schizophrenia (CDSS), Clinical Global Impression (CGI) and Heinrich's Quality of Life Scale (QLS). We are using this broad battery of tests to compare treatment groups at baseline and to allow exploratory analyses to help us understand the effects of DCS on our primary outcomes and to guide selection of outcome measures for future studies. The clinical battery will be administered at baseline and weeks 4, 8, 12, 24, and, in most subjects,

Study #:S12-02991

36. In addition, the Delusion Subscale of the PSYRATS will be administered at weeks 2, 3, 6 & 10 to assess the time course of DCS effects on delusions. Ratings will be performed prior to the DCS/CBT session each week. Additionally, the Drug and Alcohol Questionnaire and the Pittsburgh Sleep Quality Index will be performed at baseline. Assessment of cognitive functioning will be measured by the MATRICS battery at baseline only since we have found no effect of daily or weekly DCS administration on this and similar cognitive batteries in four randomized controlled trials. The SAFTEE will be administered at weeks 3, 4, 8, and 12. The SAFTEE is a self-report measure on which the participant rates the severity of 55 side effects on a 4 point Likert Type scale. The scale also asks the participant to furnish an overall rating on the severity of all side effects. Participants will be followed regardless of whether they remain on study drug or comply with CBT sessions to permit an unbiased causal estimate of D-cycloserine treatment efficacy under the intention-to-treat principle. Additionally, a per protocol analysis will be performed using data only from subjects who have substantially complied with the protocol.

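### The PSYRATS rating taken after the DCS-free CBT lead-in has no baseline role: the primary model loses precision, and lead-in change can count toward 20% response

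*Combined protocol and SAP*

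**What the plan says.** - **Baseline.** The Assessments section has the SAPS done "at screening and four weeks later at baseline to identify subjects with persistence of sufficient delusional severity to enter the study", so baseline is the entry visit. The Analysis Plan (Primary) says "Baseline PSYRATS will be included in the model together with a baseline by treatment interaction term" and names no other PSYRATS score as baseline.
- **Lead-in.** CBT/DCS Protocol gives study drug with sessions 3 to 12 and says "Placebo will be administered prior to sessions 1 & 2". The rationale for the protocol design says "we will begin with two introductory sessions unaccompanied by study drug". The two sections differ on whether a capsule is given and must be reconciled, but on both neither arm receives DCS before session 3.
- **Ratings around the first dose.** Beyond the full battery, "the Delusion Subscale of the PSYRATS will be administered at weeks 2, 3, 6 & 10", and "Ratings will be performed prior to the DCS/CBT session each week".
- **Response.** The persistence hypothesis in Specific Aims is "maintenance of a 20% or greater reduction in the PSYRATS Delusions Subscale total score from baseline". The onset hypothesis, the responder model and the cure model use a 20% reduction or refer to response without naming a reference score. The onset hypothesis concerns response once DCS has been given for two weeks. The responder comparison in the Secondary analysis opens at week two.

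**The concern.** The trial asks what DCS adds to CBT, and the protocol deliberately starts with two sessions without DCS. A PSYRATS score taken after those sessions and before the first differing dose is closer in time to week 12 than the entry score. It also already contains any change from CBT engagement, placebo or regression to the mean. The plan uses it neither as a covariate nor as the response reference.

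Two things are at stake. The primary contrast may carry residual variance that an already scheduled rating could remove. And where response is measured from entry, a subject can go part or all of the way to 20% before any DCS. Because the responder comparison opens at week two, an onset could be dated before the first DCS dose. Moving that opening week alone would not solve this, since the reference score would still precede the lead-in.

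**Working it through.** **1. The plan's own power (Estimation of statistical power).** Inputs: 60 evaluable subjects, 1:1, so 30 per arm; effect size 0.8; two-sided 0.05. Normal approximation: 0.8 × √(30/2) = 3.098; 3.098 − 1.960 = 1.138; power 87.3%. The noncentral t gives 86.1%. Both agree with the stated figure of more than 85%. For response of 10% against 50%, the pooled formula gives 94.3% and the unpooled 96.4%, against a stated figure above 95%. The means calculation uses no covariate, so the choice of baseline does not make it wrong.

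**2. When the first dose falls.** The sections do not agree.
- Assessment of memory consolidation has story B given at week 3, one hour after study drug, as the test of the first dose. Ratings precede the session, so the week-3 PSYRATS would be pre-dose.
- The payment list pays, in dollars, "30 for the screening visit, visits 3, 7, 11, 15, 16, and 17". Visits 3, 7, 11, 15, 16 and 17 line up with baseline and weeks 4, 8, 12, 24 and 36, which would make visit 6 week 3. The list carries no week labels, so it is consistent with this reading but does not prove it.
- Estimation of statistical power describes the week-3 assessment as the first one after study drug, which puts the dose earlier.
- Assessment of cognitive flexibility refers to a week-2 administration of the exercise that elsewhere accompanies the first dose.
- The memory section states a two-week gap between stories A and B. Story A one week before baseline and story B at week 3 would be four weeks apart if baseline is week 0.

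Entry to first dose is thus about three weeks on one reading and about two on the other. Two CBT sessions precede the dose on both. The last pre-dose rating would be week 3 or week 2 accordingly.

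**3. Precision at week 12.** The documents give no correlations, so these are assumed. Let r0 be the correlation of the entry score with week 12, and r3 that of the last pre-dose score. Using the later score in place of the earlier multiplies residual variance by (1 − r3²)/(1 − r0²). Power is for 30 per arm with SD √(1 − r²).

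| r0 / r3 | variance ratio | power, d = 0.8 | power, d = 0.5 |
|---|---|---|---|
| 0.3 / 0.4 | 0.91→0.84: 0.92 | 90.1% to 92.2% | 52.8% to 56.1% |
| 0.5 / 0.6 | 0.75→0.64: 0.853 | 94.7% to 97.2% | 60.9% to 67.7% |
| 0.5 / 0.7 | 0.75→0.51: 0.68 | 94.7% to 99.1% | 60.9% to 77.4% |
| 0.5 / 0.5 | 1.00 | no change | no change |

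A simulation (r0 = 0.5, r3 = 0.65, correlation 0.7 between the two scores, true effect −0.8) gave mean estimates of −0.81 with the entry covariate and −0.80 with the pre-dose covariate. The standard errors were 0.227 and 0.200, and 0.201 with both covariates. The cost is precision, not bias. With complete data and visit-specific treatment terms, keeping the pre-dose ratings as outcome visits does not recover it at week 12.

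**4. The 20% threshold.** If the lead-in lowers the score by x%, the further fall needed from the pre-dose score is (20 − x)/(100 − x): 15.8% for x = 5, 11.1% for x = 10, 5.9% for x = 15.

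**5. Dilution of the response difference.** Suppose a share f of both arms already meets the criterion before DCS and stays there. Each rate p becomes f + (1 − f)p. Power uses the pooled formula, 30 per arm.

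| f | placebo / DCS | power |
|---|---|---|
| 0 | 10% / 50% | 94.3% |
| 5% | 14.5% / 52.5% | 89.7% |
| 10% | 19% / 55% | 84.1% |
| 20% | 28% / 60% | 71.5% |

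**6. How large f might be.** Assume true scores N(16, 3), rating-error SD 1.5 to 2 and a lead-in fall of 1 to 2 points. Then 14% to 32% cross 20% at one pre-dose rating. The Secondary analysis, however, requires onset to hold to the end of treatment. With a flat true score afterwards and independent errors, only about 0.6% to 3.8% hold 20% at all of weeks 3, 4, 6, 8, 10 and 12. Continuing improvement or differing individual courses would raise this.

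**The case against.** The strongest reply is that an entry baseline is legitimate. The primary aim concerns a 12-week course of CBT and the plan tests a 12-week decline, which an entry baseline matches. Randomization protects the contrast. At the planned effect of 0.8, the 0.5/0.6 case moves power only from 94.7% to 97.2%. All of this stands, and it makes the point one of efficiency and endpoint definition rather than validity.

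Four stronger readings are tempting, and the documents do not support them.
- *Lead-in change biases the primary result.* It does not: both arms share it, so it cancels in the week-12 contrast. The severity gate is on the SAPS, not on PSYRATS, and needs two assessments four weeks apart, which limits regression to the mean.
- *Every response definition is measured from entry.* The plan says so only for persistence. For onset, the responder model and the cure model the reference is unstated.
- *Up to a third of subjects would be counted as responders before DCS.* That is a single crossing under assumed values. Under the sustained-onset rule and a flat later course it is about 0.6% to 4%. With no lead-in fall at all, 6% to 11% cross once through rating error alone, which a later reference does not remove.
- *The week-3 rating is certainly pre-dose.* The power section contradicts this. If week 3 is in fact post-dose, adjusting for it or measuring response from it would remove part of the first-dose effect.

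**Conclusion.** The concern holds as a loss of precision in the primary analysis and a gap in the response definitions. The week-12 contrast is unbiased. The variance saved is about 15% if correlations with week 12 are 0.5 at entry and 0.6 pre-dose, 8% to 32% over the unequal pairs shown, and about zero if they are equal; all of these are assumptions.

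For response, lead-in improvement counts toward 20% where the reference is entry, explicitly for persistence and by inference elsewhere. An onset could also be dated before any DCS, which does not match a hypothesis about response after two weeks of DCS. The size of this cannot be fixed from the documents, which give no PSYRATS SD, correlations or lead-in change. The power losses in step 5 show what would follow from a given f; they do not estimate it.

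**What to change.** 1. Reconcile the memory-consolidation, cognitive-flexibility and statistical-power sections on when the first study-drug dose falls relative to the week-3 rating. Until then, tie the rule to the dose and not to a named week.
2. In the primary MMRM, add the last PSYRATS Delusions score taken before the first randomized DCS/placebo dose (session 3) as a covariate beside the entry baseline. Use the entry score as the fallback where it is missing. Remove pre-dose ratings from the outcome visits.
3. For onset and response, count only ratings after that dose and use the same last pre-dose score as the 20% reference. State the reference in each definition, including persistence and the cure model. Report response from the entry baseline as a sensitivity analysis.

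The cost is plan wording, since the ratings are already scheduled. Response rates will look lower in both arms because lead-in improvement no longer counts, and one extra covariate degree of freedom is used.
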